Study Protocol and Statistical Analysis Plan

Culturally Tailoring an Advance Care Planning Intervention for American Indians

ID: 1685879-1

June 30, 2024

Study Aims

This project had three specific aims: 1. Culturally tailor the content of the Make Your Wishes About You (MY WAY) ACP curriculum and guide for one American Indian Tribe; 2. Assess the feasibility of the culturally tailored MY WAY ACP curriculum and patient education guide with the tribe; and 3. Examine the preliminary outcomes of the culturally tailored MY WAY ACP curriculum guide with 70 tribal members.

Study Protocol

Study Design

We used a quasi-experimental waitlist-controlled study design to test the hypothesis that after participating in the tailored MY WAY intervention, participants would experience decreased ACP barriers and increased ACP facilitators, readiness, self-efficacy, and completion. This design split our total participant pool into two cohorts to allow for a comparison group while still providing the intervention to all participants. Cohort 1 received the intervention immediately after study enrollment and served as the intervention group. Results from Cohort 1 were then compared to the waitlisted cohort, or Cohort 2, who waited over 3 months on average to receive the intervention.

Intervention

The intervention consisted of two steps: attendance at a Community Information Session (CIS) and attendance at an individual Sharing Session (SS).

Recruitment

Study eligibility criteria included being an enrolled Tribal member, spouse of a Tribal member, first descendant, or a member of another AIAN Tribe, aged ≥ 18 years, and residing within the Tribal service area. We recruited potential participants using convenience sampling

techniques. We made in-person study recruitment announcements at 13 Tribal venues and left flyers and hung posters at 26 locations. We also ran an ad in the Tribal newspaper and on three billboards. Tribal programs distributed MY WAY information on our behalf via their social media and/or email listserv. We also developed a project website and ran a short video on the local Tribal television station. Interested people were directed to call the Project Coordinator by telephone and/or speak with staff at a CIS and then screened for study eligibility and enrolled, if eligible.

Data Collection

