All study participants completed informed consent documents before study participation and all who completed the full intervention and the interviewer-administered surveys received \$85 in gift card incentives. Data were collected via surveys from Cohort 1 immediately before the CIS (“intervention baseline survey”), 8-9-weeks after the CIS at posttest (“post-program survey”), and 6-month follow up (“follow-up survey”). For Cohort 2, survey data was collected at baseline (“control baseline survey”), an average of 13 weeks immediately before CIS attendance (“intervention baseline survey”), and an average of 12-weeks after the CIS (“post-program survey”). The first survey administered with Cohort 2 participants occurred at study enrollment and served as a control baseline comparison to Cohort 1.

Measures

ACP barriers and facilitators were assessed with 16 yes/no questions (8 barriers and 8 facilitators) derived from qualitative data regarding ACP and developed during the original MY WAY clinical trial, but never published.

ACP readiness and self-efficacy were captured with the 9-item ACP Engagement Survey Process Measures identified from Behavioral Change Theory. The 6-item readiness and

the 3-item self-efficacy subscales have 5-point, Likert responses of “not at all, a little, somewhat, fairly, extremely.” In a field test of these subscales, they demonstrated good reliability and discriminant validity (Sudore et al., 2017; 2013).

For **ACP completion**, participants were asked if they had a legal advance directive. To confirm self-reports post-program, project staff documented whether the participant’s advance directive was notarized after SS and compared this to notary records. All sources of the participant’s advance directive completion measure were combined into a single binary variable (yes/no).

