Interview-administered intervention and control baseline surveys also included self-reported demographic characteristics of age (in years), gender (male or female), marital status (married or not married), Tribal affiliation (member, first descendent, family of a member, member of another Tribe), education (on a scale of 1 = less than high school education to 5 = graduate degree), self-rated health (on a scale of 1 = very poor to 6 = excellent), and self-reported diagnosis of any chronic conditions. Chronic conditions included chronic obstructive pulmonary disease, history of stroke, history of heart attack, cancer, chronic kidney disease, type 2 diabetes, heart disease, high cholesterol, and chronic pain.

Analyses

All analyses were conducted in IBM SPSS Statistical Software (27) or Microsoft Excel. We examined participant demographic characteristics using descriptive statistics and stratified analyses. To determine if there were demographic or other differences between the cohorts, we conducted crosstabulation analyses with Bonferroni correction applied. To compare intervention baseline and post-program levels of barriers and facilitators, as well as analyze change over time in ACP readiness, self-efficacy, and completion, we combined the cohorts. As barriers and

facilitators were asked as simple “yes/no” questions, the number of barriers and facilitators listed by participants was calculated before and after the intervention for comparison.

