Before combining the individual readiness and self-efficacy items, we ran selectivity and reliability analyses. To check for differences in the sample due to attrition, we computed Little's missing completely at random (MCAR) test. We then conducted crosstabulations again to look for relationships between demographic characteristics and ACP readiness, self-efficacy, and completion measures at intervention baseline. With our combined sample, we conducted a 3 (readiness, self-efficacy, and completion) x 2 (pretest to 8-week posttest) way repeated measures analysis of variance (ANOVA) with demographic characteristics found to be related to intervention baseline measures as between-subjects variables. For 6-month follow-up surveys with Cohort 1, we conducted a separate one-way ANOVA (intervention baseline, post-program, follow-up) for ACP readiness and self-efficacy. We tested the hypothesis that Cohort 2 participants did not change ACP-related readiness and self-efficacy from control baseline to intervention baseline by conducting a third separate one-way repeated measures ANOVA. We also calculated difference scores from control baseline to intervention baseline among Cohort 2 participants and intervention baseline to post-program among all participants.

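### Cohort 2's waiting period is judged by an ordinary significance test that can detect drift but cannot support the stated hypothesis of no change; the mean change should be reported with its 95% CI

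*Combined protocol and SAP*

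**What the plan says.** The Study Design section presents Cohort 2 as the comparison group: "Results from Cohort 1 were then compared to the waitlisted cohort". Under Data Collection, Cohort 2 is surveyed at enrolment (control baseline), again just before the information session (intervention baseline), and again after it. The first gap is given as "an average of 13 weeks immediately before CIS attendance"; the post-program survey follows the session by 12 weeks on average.

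The Analyses section then states, for the wait: "We tested the hypothesis that Cohort 2 participants did not change ACP-related readiness and self-efficacy from control baseline to intervention baseline", and names the method: "by conducting a third separate one-way repeated measures ANOVA". The next sentence adds an estimate: "We also calculated difference scores from control baseline to intervention baseline among Cohort 2 participants and intervention baseline to post-program among all participants".

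No confidence interval, margin, significance level or Cohort 2 sample size is given. The intervention-period difference score is described for the whole sample, not for Cohort 2 alone.

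**The concern.** The hypothesis the investigators set out for the wait is stability, and the named test has stability as its null. Such a test can contradict the hypothesis but has no outcome that supports it. A large p-value may mean that nothing drifted, or that the cohort was too small to show that something did.

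This matters because of where the test sits. The pre-post analysis combines the cohorts, and the Analyses section specifies no between-cohort test of change in the outcomes. That leaves the waiting-period ANOVA as the only specified test of change in readiness and self-efficacy without the intervention. If a reader takes its p-value alone as the control evidence, that evidence may look firmer than it is.

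**Working it through.** The plan gives no power, sample-size or precision figure to reproduce for this test, so the check starts from its form.

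**Form of the test.** Control baseline and intervention baseline are two time points. Taking one analysis per outcome, a one-way repeated measures ANOVA on two time points equals a two-sided paired t-test, F(1, n−1) = t². The null is a mean change of zero. The mismatch with the stated hypothesis follows from this alone and needs no assumed numbers.

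**Inputs for the size.**
- Study Aims: 70 members in total. The split is not stated. Half of 70 is 35, with no loss; 20 to 40 analysed is taken as the range (assumption).
- Two-sided 5% level (assumption).
- True drift d of 0.3 or 0.5 SD of the change score (illustrative; the documents give no SD and no drift size).

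**Formulas.**
- P(non-significant) = P[F(1, n−1; λ) < t²(0.975, n−1)], with noncentrality λ = n·d².
- 95% CI half-width, in SDs of change = t(0.975, n−1)/√n.

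For n = 35 and d = 0.3: λ = 35 × 0.09 = 3.15 and the critical F is 2.032² = 4.13, so P(non-significant) = 0.59. The half-width is 2.032/5.916 = 0.34.

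| n analysed in Cohort 2 | Non-significant, d = 0.3 | Non-significant, d = 0.5 | 95% CI half-width (SD) | Drift detectable with 80% power (SD) |
|---|---|---|---|---|
| 20 | 75% | 44% | 0.47 | 0.66 |
| 35 | 59% | 18% | 0.34 | 0.49 |
| 40 | 54% | 13% | 0.32 | 0.45 |

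As an outer bound, if all 70 had been in this test, a drift of 0.3 SD would still be non-significant 30% of the time.

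**Within-person contrast.** With scores Y1 (control baseline), Y2 (intervention baseline) and Y3 (post-program), the intervention-period change minus the waiting-period change is (Y3 − Y2) − (Y2 − Y1) = Y3 − 2·Y2 + Y1.
- Precision: with equal variances and equal correlations, its variance is 6(1−ρ)σ² against 2(1−ρ)σ² for one change, a ratio of SDs of √3 = 1.73. With first-order autoregressive correlation r the ratio is √(3−r), which is 1.52 at r = 0.7. At n = 35 the half-width is therefore 0.344 × 1.52 to 0.344 × 1.73, or 0.52 to 0.60 SD of a single change.
- Regression to the mean: an error e in Y2 moves the first change by +e, the second by −e and the contrast by −2e. A chance shortfall of 0.1 points at intervention baseline adds 0.2 points to the contrast.
- It also assumes that drift would have continued at the waiting-period rate.

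**The case against.** The best defence is that nothing has been misread. The sentence can be taken as a plain statement of the null, which is how such a test is set up, and a significant result would have been valid evidence of drift. The plan does not rest on a p-value alone either, since the waiting-period difference score was calculated. The aim is modest ("Examine the preliminary outcomes of the culturally tailored MY WAY ACP curriculum guide with 70 tribal members"), and no decision is tied to this test. The non-significance rates depend on an assumed cohort size and on the drift chosen: at 0.5 SD and n = 35 the rate is only 18%.

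Most of this stands, and it sets the limits of the point. The test is a legitimate drift check, and the estimate that is needed already exists. What remains is that the estimate is described without an interval, that the intervention-period score is not described for Cohort 2 alone, and that the named test cannot support the hypothesis attached to it.

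A reader might infer more: that a non-significant result was taken as proof of stability, or was used to justify combining the cohorts. The documents support neither. They do not say how a non-significant result was interpreted, and they give this test no stated role in the decision to combine.

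**Conclusion.** The point holds in a limited form and is minor. The two-time-point ANOVA can reveal drift during Cohort 2's wait, but a non-significant result would not support the stated hypothesis. That conclusion depends on no assumption. Its practical size does: with 20 to 40 analysed and a two-sided 5% level, a drift of 0.3 SD of change would go undetected in about 54% to 75% of such studies and 0.5 SD in about 13% to 44%. The mean change would be known to within 0.32 to 0.47 SD either way.

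The defect lies in the plan as worded, not in any conclusion the documents draw. The absence of a specified between-cohort test of outcome change is a separate matter and is not argued here.

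**What to change.** 1. Report Cohort 2's waiting-period difference score as a mean change with its 95% CI, separately for readiness and self-efficacy, and state the number analysed.
2. Set beside it Cohort 2's own intervention-period mean change with its 95% CI, as well as the score for all participants.
3. Make no claim of no change. No margin was set in advance, and none can now be.
4. Optionally, add the within-person contrast with its 95% CI as a supportive estimate only. State with it the lower precision, the exposure to regression to the mean through the shared intervention-baseline score, and the assumption of constant drift. Before relying on the two periods being of similar length, reconcile the 12-week average for Cohort 2's post-program survey under Data Collection with the 8-week label given to the posttest under Analyses.

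The cost is a change of wording and a small re-analysis of data already collected. The downside is that the intervals may be wide and the control evidence may turn out inconclusive, which is acceptable for a study of preliminary outcomes.

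### Completion is hypothesised in a waitlist-controlled design, but its only named test of change is an uncontrolled combined-cohort pre-post ANOVA; no test compares change between cohorts for any outcome

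*Combined protocol and SAP*

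**What the plan says.** Study Design describes a "quasi-experimental waitlist-controlled study design". Its hypothesis covers five outcomes: barriers, facilitators, readiness, self-efficacy and completion. It adds that "Results from Cohort 1 were then compared to the waitlisted cohort", without naming an outcome or a method. Data Collection says Cohort 2's enrolment survey "served as a control baseline comparison to Cohort 1". Recruitment says "We recruited potential participants using convenience sampling", and no random assignment to cohort is described.

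Measures defines completion as a single yes/no variable. After the programme, self-reports were checked: staff recorded whether the "advance directive was notarized after SS and compared this to notary records". The SS is the individual Sharing Session, the second step of the intervention.

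Analyses pools the cohorts to "analyze change over time in ACP readiness, self-efficacy, and completion, we combined the cohorts". It then describes three ANOVAs. The combined-sample 3 x 2 pre-post model includes completion. The Cohort 1 six-month model covers readiness and self-efficacy. The Cohort 2 wait-period model tests whether participants "did not change ACP-related readiness and self-efficacy from control baseline to intervention baseline". The section ends with difference scores over the Cohort 2 wait and over the pre-post period for everyone, with no outcome listed and no test attached.

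**The concern.** A waitlist arm exists to show how much change occurs without the programme. Once the cohorts are pooled and no cohort factor is stated, a pre-post test counts every directive completed between the two surveys, whatever prompted it. The plan checks the wait period for readiness and self-efficacy but names no such test for completion, which is in the same hypothesis.

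The gap is wider than completion. Barrier and facilitator counts also have no named wait-period test, and the comparison of cohorts stated in Study Design is not specified for change in any outcome. Completion deserves particular attention for a reason that is an inference and is not in the documents: people seldom give up a directive once they hold one, so background uptake would push the pre-post change upward. At stake is how far a reported rise in completion can be credited to the programme.

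**Working it through.** **1. Which analysis of change names which outcome (Analyses section)**

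| Analysis | Sample | Contrast | Completion named? |
|---|---|---|---|
| 3 x 2 repeated measures ANOVA | Both cohorts combined | Pre to post | Yes |
| Separate one-way ANOVA | Cohort 1 | Baseline, post, 6 months | No |
| Separate one-way ANOVA | Cohort 2 | Control baseline to intervention baseline | No |
| Difference scores | Cohort 2; then all participants | Wait; then pre to post | No outcome named, no test |

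Completion is in 1 of 3 tests of change and in 0 of 1 wait-period tests. The Bonferroni-corrected crosstabulations address demographic or other differences between cohorts, not change. The later crosstabulations that name completion concern its relation to demographics at intervention baseline. No row contrasts change in Cohort 1 with change in Cohort 2.

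**2. What background uptake could add.** Only the 70 comes from the documents (Study Aims). Numbers without a directive and uptake rates are assumed.

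Added points = uptake x (number at risk / 70) x 100.

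| At risk of 70 | 2% uptake | 5% | 10% |
|---|---|---|---|
| 42 | 1.2 | 3.0 | 6.0 |
| 56 | 1.6 | 4.0 | 8.0 |
| 63 | 1.8 | 4.5 | 9.0 |

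Example: 0.05 x 56/70 = 0.04, or 4.0 points.

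**3. What the wait-period figure could show.** Exact (Clopper-Pearson) two-sided 95% limits, with assumed numbers at risk in Cohort 2. For zero events the upper limit is 1 - 0.025^(1/n).

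- 0 of 28: upper limit 12.3%
- 0 of 35: upper limit 10.0%
- 1 of 28: 0.1% to 18.3%
- 3 of 28: 2.3% to 28.2%

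**4. Cap on the background share if 0 of 28 completed during the wait.** The windows differ: a wait averaging about 13 weeks, post-program at 8-9 weeks in Cohort 1, and "an average of 12-weeks after the CIS" in Cohort 2. At a constant rate, uptake over t weeks is 1 - (1 - r)^(t/13), with r = 0.1234.

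- Cohort 1, t = 8.5: 1 - 0.8766^(8.5/13) = 0.0825
- Cohort 2, t = 12: 1 - 0.8766^(12/13) = 0.1145
- With 28 at risk in each cohort: (28 x 0.0825 + 28 x 0.1145)/70 = 0.079, about 7.9 points

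Unscaled, 0.1234 x 56/70 gives 9.9 points, but that applies a 13-week rate to shorter windows. Both figures assume that the cohorts share a background rate and that waiting does not change uptake.

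**5. Precision of a contrast between cohorts.** With assumed counts and Newcombe 95% intervals, 11/28 v 3/28 is 29 points (6 to 48), and 8/28 v 3/28 is 18 points (-3 to 38).

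**The case against.** Four points can be made for the plan.

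- **The difference scores may already cover completion.** They span the right two periods and are not restricted by outcome. The control baseline survey is said to have included demographics as an additional element, which suggests that it carried outcome items too. This stands. A reader might infer that completion was left out of the wait-period work, or that the plan necessarily yields an uncontrolled completion effect; the text supports neither. It shows only that no named test supplies the control and that the scope of the scores is unstated.
- **Notary records tie some directives to the programme.** Those recorded as notarised after the SS follow programme contact in time. That is useful and should be reported. It does not say how many of those people would have completed a directive anyway.
- **The aim is preliminary and the design openly quasi-experimental.** This lowers the stakes and argues against making a non-randomised risk difference the main result. It does not explain why the wait period was tested for two hypothesised outcomes and not the others.
- **The sizes are arithmetic on chosen inputs.** This is true. They show what background uptake could do, not that it occurred.

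**Conclusion.** The point holds as one of specification and attribution. The named completion test cannot separate background uptake from programme effect, and the between-cohort comparison stated in Study Design has no named test of change for any outcome.

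The size is unknown, because the documents give no uptake rates, cohort sizes or numbers at risk. Under the assumed inputs, background uptake would contribute 1.2 to 9.0 points to the pre-post change, which matters for a small rise and little for a large one. The wait-period figure would bound the background share loosely: no completions among an assumed 28 would still allow 12.3% over the wait, or about 7.9 points of the combined change after scaling for window length, given a constant rate shared by both cohorts and unaffected by waiting.

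A reader might go further and infer that the completion result is biased. The documents do not show that.

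**What to change.** 1. **Main addition.** Among Cohort 2 participants with no directive at control baseline, report new self-reported completion by intervention baseline (about 13 weeks) with an exact 95% interval. Set it beside the pre-post completion change measured by self-report among those with no directive at intervention baseline. Self-report keeps measurement alike, since notary confirmation is described only post-program. Show the notary-verified variable and the number notarised after the SS alongside.
2. **Difference scores.** Name the outcomes they cover.
3. **Cohort 1 versus Cohort 2.** Any risk difference should be secondary and descriptive. State that random assignment is not described, that the windows differ (8-9 v 13 weeks), that waiting participants may defer completion, and that precision is low. Deferral would understate background uptake and inflate the contrast. The longer wait works the other way: at a constant rate, 5% or 10% over 13 weeks is 3.3% or 6.7% over 8.5 weeks.
4. **Fallback.** If completion was not asked at both Cohort 2 surveys before the CIS, describe the completion change as uncontrolled.

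The cost is a short re-analysis of existing answers, provided the question was asked at both surveys, which the documents do not say. The price is reliance on less verified self-report for the comparison, and an interval that will be wide.

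### Wait-period change is scored in Cohort 2 alone and intervention-period change in both cohorts pooled, and no described analysis tests whether the second exceeds the first

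*Combined protocol and SAP*

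**What the plan says.** The last sentence of the Analyses section defines two scores: "We also calculated difference scores from control baseline to intervention baseline among Cohort 2 participants and intervention baseline to post-program among all participants". The first is the change over the wait, in Cohort 2 only. The second is the change over the intervention with both cohorts together. The sentence does not name the outcomes, and it does not say whether the two scores were compared.

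The Data Collection section gives the windows. Cohort 1's post-program survey came "8-9-weeks after the CIS at posttest". Cohort 2's wait is put at "an average of 13 weeks immediately before CIS attendance" and its post-program survey at "an average of 12-weeks after the CIS". The 13-week phrase is awkward, but the Study Design section supports it by describing Cohort 2 as those "who waited over 3 months on average to receive the intervention".

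The other change analyses in the Analyses section are:
- a repeated measures ANOVA on the combined sample, with no cohort factor named and the posttest labelled as 8-week for everyone;
- a three-time-point ANOVA in Cohort 1 alone;
- an ANOVA of Cohort 2's wait period alone, for readiness and self-efficacy.

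The Study Design section says that Cohort 1's results were compared with the waitlisted cohort. The Analyses section describes no test of change that does this.

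**The concern.** A waitlist is there to show what happens to scores without the intervention, so that the change seen with it can be judged against that. This requires a direct test of one change against the other. The document describes an uncontrolled pre-post change in everyone and, separately, a test of whether Cohort 2 changed while waiting. A non-significant result for the wait beside a significant pooled result does not show that the two changes differ.

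The two difference scores invite the missing comparison but do not supply it. The intervention score includes Cohort 1, who do not appear in the wait score. Recruitment was by convenience sampling, the design is quasi-experimental and no randomisation is described. A gap between the scores could therefore reflect a different response in Cohort 1, or windows of different length, as well as the intervention. Meanwhile Cohort 2 was surveyed at enrolment, just before the CIS and about 12 weeks after it. The same people thus provide a wait and an intervention period of nearly equal length, and that contrast is not described.

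**Working it through.** The document gives no cohort split, standard deviation, effect size or sample-size calculation, so there is no stated figure to reproduce. What can be checked is who enters each score, how long each window is, and how much the mismatch could matter under stated assumptions.

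**Inputs.** From Data Collection: wait 13 weeks; intervention window 8 to 9 weeks (Cohort 1) and 12 weeks (Cohort 2). From Study Aims: 70 participants. Assumed: Cohort 2's share of the sample, s, between 0.3 and 0.7.

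**1. Wait length.** 13 × 7 / 30.4375 = 2.99 months, close to the Study Design statement of more than three months.

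**2. Pooled window** = (1 − s) × (8 to 9) + s × 12 weeks.

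| s | Pooled window (weeks) | Shortfall against 13 weeks |
|---|---|---|
| 0.3 | 9.2 to 9.9 | 3.1 to 3.8 |
| 0.5 | 10.0 to 10.5 | 2.5 to 3.0 |
| 0.7 | 10.8 to 11.1 | 1.9 to 2.2 |

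At the extremes, 13 / 11.1 = 1.17 and 13 / 9.2 = 1.41, so the wait is 17% to 41% longer. Within Cohort 2, 13 / 12 = 1.08, or 8%.

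**3. Effect of drift.** With linear drift of g points per week, the pooled-minus-wait gap is shifted by (pooled window − 13) × g. Assume g = 0.02, s = 0.5 and Cohort 1 at 8.5 weeks: the window is (8.5 + 12) / 2 = 10.25, and the shift is (10.25 − 13) × 0.02 = −0.055 points. Within Cohort 2 it is (12 − 13) × 0.02 = −0.020. With upward drift, both shifts make the intervention look weaker. With no drift, both are zero.

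**4. Effect of cohort make-up.** The pooled change departs from Cohort 2's own change by (1 − s) × (Cohort 1 change − Cohort 2 change). If the cohorts' changes differ by an assumed 0.3 points, this is 0.5 × 0.3 = 0.15 at s = 0.5, and 0.09 to 0.21 for s from 0.7 to 0.3. Its direction is unknown.

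**5. Overlap and precision.** Assume N = 70, 35 per cohort, SD of each change 1, and correlation −0.25 between a Cohort 2 member's two changes.
- Pooled minus wait, overlap allowed for: √(1/35 + 1/70 + 2 × 0.25/70) = 0.224.
- The same, wrongly treated as independent: √(1/35 + 1/70) = 0.207.
- Own-control contrast in Cohort 2: √((2 + 2 × 0.25)/35) = 0.267.

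**6. What the wait-period test can show.** On the same assumptions, the SE of the mean wait change is 1/√35 = 0.169, so its 95% interval extends about 1.96 × 0.169 = 0.33 SD either way. A non-significant result would not establish the absence of drift.

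**The case against.** The strongest objection is that the text says only that both scores were calculated. A reader might infer that the sponsor formally compared them, but no test, interval or comparison between them is named. This stands, so the point is an omission and not a faulty test. It does not remove the point: if the scores were never compared, no controlled contrast of change is described at all.

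A reader might also infer that Cohort 2's own-control contrast is the only analysis that removes stable differences between people. It is not. Any within-person change cancels stable differences in level, including the pooled ANOVA and a comparison of Cohort 1's change with Cohort 2's wait change. The own-control contrast goes further only in also holding constant who is responding, and so stable differences in trend or responsiveness.

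Nor does the overlap rule out a valid interval. A mixed model or a person-level bootstrap handles the covariance.

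The document gives cohort make-up some attention. It checks for differences between cohorts with Bonferroni correction, and it enters demographics related to baseline measures into the combined model. These steps help with measured characteristics but supply no control-period contrast.

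Finally, the comparison named in the Study Design section is Cohort 1 against waitlisted Cohort 2, and one could argue that this is the larger gap. That comparison would be controlled, but it relies on non-randomised cohorts being comparable and sets 8 to 9 weeks against 13. Cohort 2's own-control contrast avoids most of both problems, at the cost of precision and of order confounding. With a preliminary aim in 70 people, this is an improvement worth making and does not invalidate the study.

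**Conclusion.** The point holds as an omission. Followed exactly, the Analyses section gives an uncontrolled pooled pre-post change and a separate look at the wait, with no estimate of the difference between them. The two difference scores cannot fill that role because they differ in people and in window, and Cohort 2 is in both.

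The timing component is small. A single percentage for the longer wait would need a cohort split that the document does not give, hence the range of 17% to 41%. Its effect depends on a drift of unknown size and, if drift is upward, would understate the intervention. The documents therefore do not support a claim that unequal windows inflate the effect. Cohort make-up could matter more, at 0.09 to 0.21 points under the assumed 0.3-point difference between cohorts. That figure is illustrative, since nothing in the document shows whether the cohorts responded differently.

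**What to change.** For readiness and self-efficacy, which the wait-period ANOVA shows were measured at both Cohort 2 baselines, add the own-control contrast. With C, I and P the control baseline, intervention baseline and post-program scores, d = (P − I) − (I − C) = P − 2I + C. Report mean d with a 95% CI. Preferably estimate it from a mixed model for Cohort 2 with the three surveys as categorical time points and all available surveys included, so that it is not restricted to people with all three.

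Report the intervention-period change separately for Cohort 1 and Cohort 2 as well as pooled, stating each window. Leave the changes undivided by weeks: the intervention is two discrete sessions, and rescaling would assume that its effect builds up linearly with time.

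The cost is analysis and reporting only, since the described surveys already supply the data. The interval will be wider than for the pooled contrast (SE 0.267 against 0.224 under the assumptions above), because only Cohort 2 is used and error in the middle survey enters with weight −2. The contrast also stays confounded with order, because the wait always comes first; the report should say so.
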